8.8.6 Application Site Examination

Application Site Examination will be conducted at Visit 2 to 8 in Part A and Visit 2 to 9 in Part B as indicated in schedule of assessment ([Table 2.1](#), [Table 2.2](#)). Application site evaluation will be conducted by comparing the skin of the application site with the baseline skin condition in each visit.

The application site evaluation will include dermatitis, pruritus, paresthesia, erythema, dryness, vesicles, irritation, papules, burning assessed by ICDRG scale (Table 8.2). An abnormal application site finding that is considered clinically significant will be recorded as AE. The investigator may consider photograph the skin condition under the consent of the subject if the investigator considered helpful for the safety assessment in the DSMB meeting (optional).

Table 8.2 Grading score by International Contact Dermatitis Research Group (ICDRG)

Grading	Morphology	Interpretation
-	No reaction	Negative
±?	Erythema only, no infiltration	Doubtful reaction
+	Erythema, infiltration, possibly discrete papules	Weak positive reaction
++	Erythema, infiltration, papules, vesicles	Strong positive reaction
+++	Erythema, infiltration, confluent vesicles	Extreme positive reactions
Ir	Different types of reactions (dermatitis, paresthesia, dryness, burning)	Irritant reaction

8.8.7 Appropriateness of Safety Assessments

Safety evaluations selected for this study are typical of those for this patient population and utilize widely accepted measures.

9 ADVERSE EVENTS

An AE is defined as any untoward medical occurrence in a patient administered a pharmaceutical product during the course of a clinical investigation. An AE can therefore be any unfavorable and unintended sign, symptom, or disease temporally associated with the use of a study drug, whether or not thought to be related to the study drug.

Each AE will be collected from the signing of the ICF until the follow-up/end-of-study visit. Adverse events that are identified at the last assessment visit (or the early termination visit) must be recorded on the AE eCRF with the status of the AE noted. All events that are ongoing at this time will be recorded as ongoing on the eCRF. If the Investigator indicates the AE is “probably”, “possibly”, or “definitely” related to the study drug, the AE must be followed until they are resolved or medically stable, or until reasonable attempts to determine resolution of the event are exhausted. The investigator should use his/her discretion in ordering additional tests as necessary to monitor the resolution of such events.

The procedures specified in [Section 9.4](#) are to be followed for reporting SAEs.

9.1 Recording Adverse Events

Adverse events are to be recorded on the AE page of the eCRF. The following information will be recorded:

- Assessment of whether or not the AE is an SAE ([Section 9.2.1](#))
- Assessment of AE intensity ([Section 9.2.2](#))
- Assessment of AE relationship to study drug ([Section 9.2.3](#))
- Action taken - categorized as dose increased or decreased, dose not changed, drug interrupted, drug withdrawn, not applicable, or unknown, as applicable
- Outcome - recorded as fatal, not recovered/not resolved, recovered/resolved, recovered/resolved with sequelae, recovering/resolving, or unknown, as applicable

9.2 Assessment of Adverse Events

The investigator will assess each AE for seriousness, intensity, and relationship to study drug.

9.2.1 Serious Adverse Events

The investigator is responsible for determining whether an AE meets the definition of an SAE. An SAE is any AE occurring from ICF signing through follow-up that results in any of the following outcomes:

- Death
- A life-threatening adverse drug experience
- Inpatient hospitalization or prolongation of existing hospitalization
- A new persistent or significant disability/incapacity
- A congenital anomaly/birth defect
- An important medical event(s)

Important medical events that may not result in death, be life threatening, or require hospitalization may be considered an SAE when, based upon appropriate medical judgment, they may jeopardize the patient and may require medical or surgical intervention to prevent any of the outcomes listed in this definition. Examples of such medical events include allergic bronchospasm requiring intensive treatment in an emergency room or at home, blood dyscrasias or convulsions that do not result in inpatient hospitalization, or the development of drug dependency or drug abuse.

Note: SAEs require immediate reporting to the Sponsor. Refer to [Section 9.4](#) for details.

9.2.2 Intensity

The intensity of an AE will be graded according to the following definitions:

- Mild: The patient experiences awareness of symptoms but these are easily tolerated or managed without specific treatment.
- Moderate: The patient experiences discomfort enough to cause interference with usual activity, and/or the condition requires specific treatment.
- Severe: The patient is incapacitated with inability to work or do usual activity, and/or the event requires significant treatment measures.

9.2.3 Relationship to Study Drug

The relationship of an AE to the study drug should be determined by the investigator according to the following criteria:

- Unrelated: This category applies to those AEs that are clearly and incontrovertibly due to extraneous causes (disease, environment, etc).
- Unlikely: This category applies to those AEs that are judged to be unrelated to the test drug/study procedure but for which no extraneous cause may be found. An AE may be considered unlikely to be related to investigational product/procedure if or when it meets

CONFIDENTIAL

2 of the following criteria: (1) it does not follow a reasonable temporal sequence from administration of the test drug/study procedure; (2) it could readily have been produced by the patient's clinical state, environmental or toxic factors, or other modes of therapy administered to the patient; (3) it does not follow a known pattern of response to the test drug/study procedure; or (4) it does not reappear or worsen when the drug/study procedure is re-administered.

- Possibly: This category applies to those AEs for which a connection with the test drug/study procedure administration appears unlikely but cannot be ruled out with certainty. An AE may be considered possibly related if or when it meets 2 of the following criteria: (1) it follows a reasonable temporal sequence from administration of the drug/study procedure; (2) it could not readily have been produced by the patient's clinical state, environmental or toxic factors, or other modes of therapy administered to the patient; or (s) it follows a known pattern of response to the test drug/study procedure.
- Probably: This category applies to those AEs that the investigator feels with a high degree of certainty are related to the test drug/study procedure. An AE may be considered probably related if or when it meets 3 of the following criteria: (1) it follows a reasonable temporal sequence from administration of the drug/study procedure; (2) it could not be reasonably explained by the known characteristics of the patient's clinical state, environmental or toxic factors, or other modes of therapy administered to the patient; (3) it disappears or decreases on cessation or reduction in dose (note that there are exceptions where an AE does not disappear upon discontinuation of the drug, yet drug-relatedness clearly exists; for example, as in bone marrow depression, fixed drug eruptions, or tardive dyskinesia); or (4) it follows a known pattern of response to the test drug/study procedure.
- Definitely: This category applies to those AEs that the investigator feels are incontrovertibly related to test drug/study procedure. An AE may be assigned an attribution of definitely related if or when it meets all of the following criteria: (1) it follows a reasonable temporal sequence from administration of the drug/study procedure; (2) it could not be reasonably explained by the known characteristics of the patient's clinical state, environment or toxic factors, or other modes of therapy administered to the patient; (3) it disappears or decreases on cessation or reduction in dose and reoccurs with re-exposure to the drug (if re-challenge occurs); and (4) it follows a known pattern of response to the test drug/study procedure.

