5.1.1 Interim Safety/ Pharmacokinetic Data Review

Subject will receive application site examination at each visit (Part A: Visit 2 to 8; Part B: Visit 2 to 9) assessed by the trained study team, using ICDRG scale. If subject experience a new or worsening localized skin reaction in the treatment area, the subject should report to the study coordinator and/or investigator during the visit. Baseline skin condition conducted at screening in the physical examination should be used as a reference for comparison. All AEs should be recorded in the eCRF

If a subject experience 1 newly arise acute inflammation of the skin (e.g. pain, transient erythema, vesiculation, severe swelling with bullae, ulceration, or even both) at the application site, and is related (at least possible) with study drug, study treatment is recommended to be interrupted. Upon resolution of the acute inflammation, subject may resume study treatment upon investigator's judgment.

After completion of 18 subjects in Part A, the DSMB will convene to review all safety and PK data. Part B will only occur if the DSMB determines that the current dose was safe and well-tolerated. Doses for Part B will be decided by the DSMB after their review of the cumulative safety data targeted for review (AEs, vital signs, clinical laboratory results, physical examination results, itch results, and application site examination results) and available PK data from Part A. Sponsor will make the final decision in an unblinded fashion.

An ad hoc DSMB meeting will be convened in the following situations:

1. In the event of 4 subjects experiencing drug related (at least possible) adverse events with at least moderate intensity after the 1st dose of study drug or any ICDRG grade of ROAT $\geq 1+$ found during the first 7 days of study treatment, ad hoc DSMB meeting will be held to review the safety data and recommend in writing to Sponsor whether to continue, modify, or stop the clinical study on the basis of safety considerations.

2. In the event of ≥ 2 subjects experiencing drug related (at least possible) adverse events with at least moderate intensity in the first 6 subjects receiving study drug after the 1st dose or any ICDRG grade of ROAT $\geq 1+$ found during the first 7 days of study treatment, ad hoc DSMB meeting will also be convened to discuss the safety events to recommend Sponsor whether to continue, modify, or suspension the enrollment of the study.

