11.1 Adverse events

All AEs will be coded using the Medical Dictionary for Regulatory Activities (MedDRA) Version 22.0 (or later).

Adverse events will be grouped by system organ class (SOC) and PT and summarised by treatment. The summary tables will present the number and percentage of subjects with AEs and number of events, by SOC and by PT for each treatment group.

All AE summaries will be restricted to Treatment-emergent adverse events (TEAEs) only.

A treatment emergent adverse events (TEAE) is defined as any AE with an onset date on or after the first dose of study treatment if the AE was absent before the first dose of study treatment, or pre-existing medical condition worsens after the first dose of study treatment.

For the summaries of AEs, subjects who experience the same AE (in terms of the MedDRA SOC and

QMS Document Name: Statistical Analysis Plan	Page 19 of 33
QMS No (include version ref): STF-015-GL.02	Document date: 09JUL2019
CONFIDENTIAL	

PT) more than once will only be counted once for that event in the number of subjects but all occurrences of the same event will be counted in the number of events.

For analysis, at AE level, the worst severity and the strongest relationship to trial treatment will be assigned to the AE if the severity and relationship changes overtime for the AE with the same AE ID. At subject level, a subject with the same AE term being reported multiple times, the maximum severity and the strongest relationship to trial treatment will be tabulated.

Study drug related TEAEs are defined as TEAEs with definitely, probably, or possibly relationship with study drug

Nature and severity of adverse event (AEs) and number of patients with AEs will be analysed as primary endpoint in part A and secondary endpoints of Part B.

An overview table of TEAEs will be provided detailing the number and percentage of subjects along with the number of reported events with

- Any TEAE
- TEAEs by severity (Mild, Moderate, Severe)
- Any TEAE related to study drug
- Any serious TEAE
- Any serious TEAE, related to study drug
- Any TEAE leading to discontinuation of study drug
- Any TEAE leading to death

Summary tables will also be provided for TEAEs, TEAE by severity, study drug related TEAEs, TEAEs leading to discontinuation of study drug, and TEAEs leading to death, detailing the number and percentage of subjects and number of events by MedDRA SOC (ordered by frequency) and PT (ordered by frequency).

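### Protocol 9.2.3 rates relationship to the study drug by criteria that also admit study procedures, so a procedure-only event can be counted as drug related (minor)

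*Protocol*

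**What the plan says.** Protocol 9.1 names one causality item for the AE page: "Assessment of AE relationship to study drug". Section 9.2.3 opens in the same terms: "The relationship of an AE to the study drug should be determined by the investigator according to the following criteria".

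The five categories that follow do not keep to the drug:

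- Unrelated is for events "clearly and incontrovertibly due to extraneous causes (disease, environment, etc" (the bracketed list ends there). Study procedures are not named.
- Unlikely is for events "judged to be unrelated to the test drug/study procedure but for which no extraneous cause may be found".
- Possibly is for events for which a "connection with the test drug/study procedure administration appears unlikely but cannot be ruled out with certainty". Two of three criteria are needed.
- Probably is for events that "the investigator feels with a high degree of certainty are related to the test drug/study procedure". Three of four criteria are needed.
- Definitely also refers to drug or procedure in its lead-in. All four criteria are needed, and its third is written in terms of dose and re-exposure to the drug.

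Two places use the rating downstream. SAP 11.1 states: "Study drug related TEAEs are defined as TEAEs with definitely, probably, or possibly relationship with study drug". Protocol 5.1.1 convenes an ad hoc DSMB meeting in the event of "4 subjects experiencing drug related (at least possible) adverse events with at least moderate intensity". A second trigger there applies the same threshold to 2 or more of the first 6 subjects. SAP 1.2 repeats both triggers.

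**The concern.** The field is named for one cause and defined by two. If raters apply the criteria literally, a needle injury or another purely procedural event becomes study drug related, including in a patient on placebo. The related-TEAE and serious-related-TEAE outputs and the trigger counts would then measure something wider than their labels say. Raters who follow the heading and raters who follow the criteria could also classify the same event differently.

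Part A has 18 patients and trigger thresholds of 2 and 4 subjects, so single events carry weight. Procedures are frequent: Table 2.3 schedules 7 PK samples per patient, or 7 × 18 = 126 draws, before laboratory sampling is counted.

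**Working it through.** **Step 1: trace a procedure-only event through 9.2.3.** Take a haematoma caused by a PK blood draw.

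| Category | Does the event fit? |
|---|---|
| Unrelated | Not clearly. The cause must be extraneous; the examples are disease and environment, with an open-ended *etc*. |
| Unlikely | Not clearly. The event must be judged unrelated to the drug or the procedure, and here the procedure is the cause. |
| Possibly | Yes. Timing (criterion 1) and known response to the procedure (the last criterion) supply the 2 needed. |
| Probably | Can fit. Criteria (1) and (4), plus (2) if no other explanation applies, supply 3 of 4. The dose criterion (3) is not needed. |
| Definitely | Normally no, because criterion (3) is in drug terms. |

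No drug effect enters this trace, so it is the same in both arms.

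**Step 2: look for a correction downstream.** Section 9.1 lists no procedure-causality item. SAP 11.1 counts Possibly or stronger as related. Both triggers in 5.1.1 use at least possible and at least moderate. Nothing in the protocol or SAP separates procedure-related from drug-related events. The ROAT limb of the triggers uses the ICDRG grade, not this rating.

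**Step 3: size the effect on the triggers.** The documents state no figure on this point, so there is none to reproduce. Let p be the proportion of patients with at least one moderate or worse procedure-only event. This is an assumption, taken over 2% to 10%.

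For 2 of the first 6: P = 1 − (1 − p)^6 − 6p(1 − p)^5.

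- p = 0.02: 1 − 0.8858 − 0.1085 = 0.0057
- p = 0.05: 1 − 0.7351 − 0.2321 = 0.0328
- p = 0.10: 1 − 0.5314 − 0.3543 = 0.1143

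For 4 subjects, 5.1.1 gives no denominator. I use the 18 patients of Part A and the binomial tail P(X ≥ 4).

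| Assumed p | 2 of first 6, procedure-only events alone | 4 of 18, procedure-only events alone |
|---|---|---|
| 2% | 0.6% | <0.1% |
| 5% | 3.3% | 1.1% |
| 10% | 11.4% | 9.8% |

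Now add truly drug-related moderate events in an assumed 5% of subjects, independent of an assumed 5% procedure-only rate. The combined rate is 1 − 0.95 × 0.95 = 9.75%. The chance of 2 of 6 rises from 3.3% to 10.9%, and of 4 of 18 from 1.1% to 9.1%.

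**Step 4: size the effect on the related-TEAE table.** Assume true drug-related rates of 10% on LT5001 and 0% on placebo, and a procedure-only rate of 5% in both arms. LT5001 reads 1 − 0.90 × 0.95 = 14.5% and placebo reads 5%. Both rates are inflated. The difference moves only from 10 to 14.5 − 5 = 9.5 points.

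**The case against.** The strongest reply is that the governing sentence and the recorded item both say study drug, and that the criteria are permissive: an event *may* be considered possibly or probably related. A reader might infer that every procedure-caused event must be rated drug related. The text does not support that. It permits and points toward such a rating without forcing it, and the open-ended *etc* under Unrelated leaves room to treat a needle injury as extraneous to the drug. The criteria still pull the other way, so the field remains ambiguous.

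The haematoma example also has a limit. These patients have in-center haemodialysis three times a week, and Protocol 8.6.2 recommends drawing blood just before dialysis. A haematoma might then be put down to another therapy, which would fail Probably criterion (2). Possibly would remain within reach. The case report form is not among the documents, so a separate procedure field cannot be excluded, although the protocol mentions none.

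A reader might also infer damage to the Part A primary endpoint. That endpoint is the nature and severity of AEs and the number of patients with them, whatever their cause, so it does not change. Nor is a treatment comparison spoiled: SAP 11.1 plans counts and percentages for TEAEs, and the risk difference in Step 4 hardly moves.

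On the triggers, the chance of at least one procedure-only event among the first 6 patients, 1 − (1 − p)^6, is 11%, 26% and 47% at the three assumed rates. It is tempting to quote these figures, but one event trips nothing. Moderate intensity also requires interference with usual activity or a need for specific treatment (Protocol 9.2.2), which a simple bruise need not meet. Reaching a trigger convenes a review that ends in a recommendation; nothing stops automatically, and the board can see what the event was. The error runs toward over-review, not a missed signal. These points hold, and they make the matter minor.

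**Conclusion.** The definition is wrong as written: 9.2.3 claims to rate the study drug but is worded for drug or procedure in four of five categories, and nothing later separates the two. A procedure-only event can be rated Possibly or Probably related in either arm. It would then count in the related-TEAE outputs of SAP 11.1 and, when at least moderate, toward the 5.1.1 triggers.

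The consequence is some inflation of related rates in both arms and a small added chance of an unneeded DSMB review. The figures in Step 3 rest on assumed event rates, on independence between patients and, for the second trigger, on a count limited to Part A. A count that ran on over more patients would give a larger chance; 5.1.1 neither says nor excludes this. The finding itself is a contradiction of definition and does not depend on these figures. Severity: minor.

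**What to change.** In Protocol 9.2.3, delete */study procedure* and */procedure* from every category and criterion, so that the field rates the study drug only. If the sponsor wants procedure causality, record it as a separate eCRF item and state that it does not feed study drug related in SAP 11.1 or the trigger counts in 5.1.1 and SAP 1.2.

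The cost is a wording change and at most one extra eCRF item. Procedure-related events stay in the all-TEAE tables, so no safety information is lost.

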9.3 Discontinuation due to Adverse Events

Any patient who experiences an AE may be withdrawn at any time from the study at the discretion of the investigator. Patients withdrawn from the study due to an AE, whether serious or nonserious, may be followed by the investigator until the clinical outcome of the AE is determined. The AE(s) should be noted on the appropriate eCRFs and the patient's progress

should be followed until the AE is resolved or medically stable as determined by the investigator. The Sponsor must be notified. If the AE relates to overdose of study treatment, the Investigator's Brochure should be consulted for details of any specific actions to be taken.

9.4 Reporting Serious Adverse Events

In the event of any SAE reported or observed during the study, whether or not attributable to the study drug, site personnel will record and report it to the Sponsor or designee within 24 hours of occurrence or when the investigator becomes aware of the event in accordance with procedures described in the SRM. If the investigator reports the SAE by telephone, a written report must follow within 24 hours including a full description of the event and sequelae in the format detailed in the SAE reporting form.

SAE Report Forms will be provided to the CRU to assist in collecting, organizing, and reporting SAEs and follow-up information.

All SAEs should be followed to their resolution, with documentation provided to the Sponsor on a follow-up SAE Report Form.

Contacts for SAE Reporting:

[REDACTED]
[REDACTED]
[REDACTED]

9.5 Pregnancy

Pregnancies will be captured if they occur in female patients from the time the patient is first exposed to the study drug until 30 days after the last exposure or the last study visit, whichever occurs later. Pregnancies in the sexual partners of male patients will be captured from the time the patient is first exposed to the study drug until 90 days after last exposure to the study drug.

Female patients must be instructed to discontinue all study drugs and inform the study investigator immediately if they become pregnant during the study.

The investigator must report any pregnancy to the Sponsor or designee within 1 business day of becoming aware of the pregnancy per pregnancy reporting procedures described in the SRM.

The patient must be immediately discontinued from further treatment with study drug. An uncomplicated pregnancy will not be considered an AE or SAE; however, all pregnancies will be followed through birth and 3 months post delivery.

Any congenital abnormalities in the offspring of a patient who received study drug will be reported as an SAE. The outcome of any pregnancy and the presence or absence of any congenital abnormality will be recorded in the source documentation and reported to the Sponsor.

